12.7. Randomisation

The unit of randomisation will be the individual participant. Site-stratified blocked randomisation, with a variable block size ranging from two to four, will be performed on a rolling basis during the recruitment period. A randomisation schedule will be defined for each health centre (study site). Within each stratum, participants will be randomised in a 1:1 ratio to either DD+ or the control group. Randomisation will be performed using REDCap or via a phone call, following the corresponding randomisation schedule.

Figure 3. Study Randomisation Summary

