15.2. Sample Size Determination

The sample size calculation for this study will be based on parameters derived from previous DIALOG+ trials (35). A standard deviation of 0.9 for the MANSA and a correlation of 0.4 between baseline and follow-up measurements will be assumed, while an effect size of 0.4 points on the MANSA will be considered the minimal clinically important difference (MCID) for quality of life in this patient population. Based on these parameters, a total of 90 participants per group will be required to achieve 90% power at the 5% two-sided significance level. To account for an anticipated 20% attrition rate, the final sample size will be set at 226 participants (113 per group).

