For the economic evaluation EQ-5D-5L will be the primary outcome. The EQ-5D-5L describes health on 5 dimensions (mobility, self-care, usual activities, pain/discomfort, anxiety/depression), each with 5 levels, yielding 3,125 possible health states denoted by a five-digit code (e.g., 11223). These health-state profiles are converted to utility weights using a Latin American value set; utilities are anchored at 1 = full health and 0 = dead, with negative values allowed for “worse-than-dead” states. This enables QALY estimation. EQ-5D-5L will be collected at baseline, 6-months and 12-months after randomisation.

There is no published Colombia-specific EQ-5D-5L value set. Therefore, in this trial we will use a Latin American value-set strategy: the Peru EQ-5D-5L value set for the base case, with Uruguay EQ-5D-5L and England EQ-5D-5L in sensitivity analyses to test robustness to the choice of tariffs.

Utilities will be assigned to each participant's EQ-5D-5L state at baseline, 6 months, and 12 months, and QALYs over 12 months will be computed using the area-under-the-curve (trapezoidal) method with linear interpolation between time points. Guidance on analysis and reporting follows (54).

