15.11.7. Analysis of cost-effectiveness

We will compute the ICER as the additional cost per additional QALY gained ($\Delta C/\Delta E$). Interpretation will use Colombia-relevant willingness-to-pay (WTP) benchmarks. Specifically, we will present cost-effectiveness acceptability curves (CEACs) across a WTP range and highlight the empirically estimated Colombia threshold of about US\$5,181 per QALY (\approx COP 17 million in 2019 prices) from Espinosa et al. (55) (IETS) updated to the study price year (2025) using DANE CPI. DIALOG+ will be described as cost-effective when the ICER lies below a WTP value deemed acceptable in Colombia, and we will report the probability of cost-effectiveness at the updated reference threshold and other policy-relevant WTP points.

Differences between trial arms in costs and outcomes will be estimated on an intention-to-treat basis, initially unadjusted and subsequently adjusted for pre-specified baseline covariates. If participant characteristics differ systematically between arms, adjusted models will include age, sex, NCD condition group (hypertension/obesity/T2DM), mental health condition group (anxiety, depression or alcohol misuse), baseline utility (EQ-5D-5L), baseline MANSA and WHOQOL-BREF, baseline total cost, and site (fixed effects).

Incremental costs will be estimated using mixed-effects generalized linear models appropriate for skewed data (primary: Gamma family with log link, or log-normal), including by random effect in the model for healthcare practitioners who delivered DIALOG+ considering clusters. Incremental cost-effectiveness will be estimated with linear mixed models including the same covariates.

Based on the results for quality of life, blood pressure control, glycated hemoglobin, and within-trial cost-effectiveness, we plan to conduct a modeled cost-effectiveness extension study over a 5-year time horizon from the healthcare perspective. In addition, a budget impact analysis with the same horizon will be carried out to support acceptability among decision-makers in the country.

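### Section 15.11.7 names its baseline covariates for costs and QALYs only under an unusable imbalance condition, which conflicts with the adjusted analysis promised one sentence earlier

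*Protocol*

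**What the plan says.** Section 15.11.7 sets out the comparison of arms in three steps.

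- Differences in costs and outcomes are estimated by intention to treat, "initially unadjusted and subsequently adjusted for pre-specified baseline covariates". No condition is attached.
- The next sentence supplies the list, but conditionally: "If participant characteristics differ systematically between arms, adjusted models will include age, sex". It goes on to the physical and mental condition groups and then "baseline utility (EQ-5D-5L), baseline MANSA and WHOQOL-BREF, baseline total cost, and site (fixed effects"). No test or threshold defines a systematic difference.
- After the cost model is described, "Incremental cost-effectiveness will be estimated with linear mixed models including the same covariates". Whether that means the conditional list is not stated.

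Section 15.11.5 defines the outcome: "EQ-5D-5L will be collected at baseline, 6-months and 12-months after randomisation", and "QALYs over 12 months will be computed using the area-under-the-curve (trapezoidal) method with linear interpolation between time points".

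Elsewhere baseline adjustment carries no condition. The primary model in Section 15.7 always contains baseline MANSA, and the secondary effectiveness models in Section 15.9 always contain the baseline value of their outcome. Section 12.7 stratifies randomisation by site, and "participants will be randomised in a 1:1 ratio to either DD+ or the control group".

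**The concern.** A covariate list that applies only after the arms have been inspected is not fixed in advance, so the two adjacent sentences cannot both be followed. The criterion also fails on its own terms. With individual 1:1 randomisation, any baseline difference is a chance difference. Read literally, the condition is never met. Read loosely, it is met whenever someone judges an imbalance large enough. For site, which is a randomisation stratum, an imbalance trigger is least suitable, because blocking within site keeps the arms close to balanced by design.

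The stake is highest for QALYs. Baseline utility is part of the QALY itself as well as a predictor of the 6- and 12-month utilities. An analysis that omits it lets a chance baseline difference pass into the incremental QALY and carries a larger standard error than necessary.

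**Working it through.** **The plan's own figure.** The protocol gives no SD, standard error or power for QALYs or costs. The only figure that can be reproduced is the primary sample size in Section 15.2: "A standard deviation of 0.9 for the MANSA and a correlation of 0.4 between baseline and follow-up measurements will be assumed", with a 0.4-point difference, 90% power and two-sided 5%.

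- With baseline adjustment: n = 2 × (1.960 + 1.282)² × 0.9² × (1 − 0.4²) / 0.4² = 2 × 10.507 × 0.6804 / 0.16 = 89.4, so 90 per group. Then 90 / 0.8 = 112.5, so 113.
- Without it: 2 × 10.507 × 0.81 / 0.16 = 106.4, so 107.

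The stated 90 is reproduced only with adjustment for baseline. The clinical side of the protocol therefore already relies on the gain that Section 15.11.7 makes conditional.

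**Inputs for QALYs.** From the documents: utilities at 0, 6 and 12 months, trapezoidal rule, 113 per arm, and a threshold of US$5,181 per QALY in 2019 prices. Assumed, not in the documents: equal utility SD (s) of 0.15 to 0.25 at each time, and a common correlation r of 0.4 to 0.6. The protocol's 0.4 is for MANSA, a different measure.

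**Formulae.**

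- QALY = 0.25·u0 + 0.5·u6 + 0.25·u12
- Unadjusted variance = s²(0.375 + 0.625r)
- Slope of QALY on baseline utility, b = 0.25 + 0.75r
- Adjusted variance = s²(0.375 + 0.625r − b²)
- SE of the arm difference = √(2 × variance / 113)

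| r | b | Unadjusted variance / s² | Adjusted variance / s² | SE ratio, adjusted to unadjusted | SE reduction |
|---|---|---|---|---|---|
| 0.4 | 0.550 | 0.6250 | 0.3225 | 0.718 | 28% |
| 0.5 | 0.625 | 0.6875 | 0.2969 | 0.657 | 34% |
| 0.6 | 0.700 | 0.7500 | 0.2600 | 0.589 | 41% |

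The ratio does not depend on s or on the number per arm. As an example, at s = 0.20 and r = 0.4 the SE falls from 0.0210 to 0.0151.

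**Effect of a chance imbalance.** The SE of the baseline utility difference is s × √(2/113) = 0.133s, which is 0.020 at s = 0.15 and 0.033 at s = 0.25. An imbalance of that size moves the unadjusted incremental QALY by b times as much: 0.020 × 0.550 = 0.011 at the low end and 0.033 × 0.700 = 0.023 at the high end. At US$5,181 per QALY, unrounded, this is about US$57 to US$121 per participant.

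**Would adjusting only on imbalance recover the loss?** Because the protocol gives no rule, take for illustration one that adjusts only when baseline utility differs at p < 0.05. In 20,000 simulated trials (113 per arm, s = 0.20), the SE under this rule was 1.29 times the always-adjusted SE at r = 0.4 and 1.53 times at r = 0.6. Never adjusting gives 1.39 and 1.70 times by the formula above. Conditional adjustment recovers only part of the loss.

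No calculation was made for costs, because the protocol gives neither a cost SD nor a correlation of baseline with follow-up cost.

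**The case against.** A reader might infer that the protocol adjusts only when an imbalance is found, or that the headline ICER will be unadjusted. The text supports neither. The sentence before the condition promises an adjusted analysis outright. The estimator named for incremental cost-effectiveness is a covariate model. Section 16 says that primary and secondary outcomes will be adjusted, and Table 1 lists cost-effectiveness as a secondary objective. The list is also fixed in advance: on the conditional reading it enters whole or not at all, so covariates are not picked one by one.

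Further points can fairly be made. The unadjusted difference is unbiased under randomisation. The 28% to 41% compares always adjusting with never adjusting, so it is not a loss that this protocol is bound to incur. Which estimate is labelled the base case can reasonably be left to an analysis plan.

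All of this stands, and it limits the claim. It does not rescue the condition. Section 16 names no covariates, and the reference to the same covariates leads back to the conditional list. The one sentence that says what adjustment means remains tied to a criterion that cannot be applied in a randomised trial.

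**Conclusion.** The point holds as a conflict in the wording with a consequence for precision. Section 15.11.7 promises adjustment for pre-specified covariates, then makes the only named set conditional on an undefined and unusable trigger, unlike Sections 15.7 and 15.9.

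On the assumed correlations of 0.4 to 0.6, with equal SDs, leaving out baseline utility costs precision: adjustment lowers the SE of incremental QALYs by 28% to 41%. The direction is firm, given the 0.25 weight on baseline utility and any positive correlation over time. The size rests on the assumptions. The dollar figures also rest on an assumed utility SD and on a threshold that the protocol will update for inflation.

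Two stronger readings should be avoided. The unadjusted estimate is not biased; the harm is chance imbalance in the realised trial and a wider interval. Nor can it be said that the cost-effectiveness conclusion would change, since the protocol gives no expected incremental cost or QALY.

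**What to change.** Delete the conditional clause in Section 15.11.7, so that the listed adjustment follows directly from the sentence before it. State that the QALY model always includes baseline EQ-5D-5L utility, that the cost model always includes baseline total cost, and that both include site as the randomisation stratum. Say that these adjusted estimates feed the base-case ICER and the acceptability curves, with the unadjusted differences reported as supportive. The gain from including site was not computed; it is there because site is a design factor.

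The cost is a change of wording. Sections 12.6 and 12.10 (Visit 2) already place EQ-5D and CSRI in the baseline assessment, and site is known for every participant.

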7. RESEARCH QUESTIONS

- In adults living in Colombia with co-existing physical and mental non-communicable diseases, does the DD+ intervention, compared to usual care, lead to quality of life improvement?
- Is the DD+ intervention implementable in the local Colombian context for patients with co-existing physical and mental NCDs, considering identified barriers and facilitators, and in terms of its feasibility, appropriateness, acceptability, adoption, and fidelity?
- In adults living in Colombia with co-existing physical and mental non-communicable diseases, does the DD+ intervention, compared to usual care, lead to enhancing social functioning and service utilisation, and in reducing depressive and anxiety symptoms?
- In adults living in Colombia with co-existing physical and mental non-communicable diseases, does the DD+ intervention, compared to usual care, lead to an improvement of clinical outcomes for diabetes, obesity or HBP?

- Does the effect of DD+ intervention in patients with co-occurring physical and mental non-communicable diseases at 6 months remain stable when the intervention frequency is reduced to every two months for the subsequent 6 months?
- What is the additional cost and cost-effectiveness of implementing and delivering the patient-centred, solution-focused intervention DD+ as part of usual care for adults with co-existing physical and mental non-communicable diseases in Colombia?

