| 
Secondary Objective (Effectiveness)
 
Evaluate the effectiveness of the DD+ intervention in enhancing social functioning and in reducing depressive symptoms and anxiety among individuals with co-existing physical and mental NCDs in Colombia.
 | 
 - Change in Social Functioning measured with Objective Social Outcomes Index (SIX) - Change in depressive symptoms, measured with Patient Health Questionnaire-8 (PHQ-8) - Change in anxiety symptoms, measured with Generalised Anxiety Disorder- 7(GAD-7) | 
 - Baseline Assessment -6-month follow-up - 12-month follow-up |
| 
Secondary Objective (Effectiveness)
 | 
 - Change in HbA1c measured through a capillary sample. | 
 - Baseline Assessment |

| | | |
|--|---|---|
| Evaluate the effectiveness of DD+ intervention in the reduction of HbA1c, systolic mmHg, diastolic mmHg, abdominal circumference and BMI | 
 - Change in systolic/diastolic mmHg measured through an automatic blood pressure cuff - Change in abdominal circumference measured with standard measuring tape | 
 -6-month follow-up- - 12-month follow-up |
| Secondary Objective (Effectiveness) Evaluate the stability of treatment when reducing the frequency of DD+ visits (bimonthly visits in the 6 to 12-month period) | 
 - Change in QoL measured by MANSA. | -12-month follow-up |
| Secondary Objective (Cost effectiveness) Assess the additional cost and cost-effectiveness for implementation and delivery of patient-centred solution-focused intervention with DD+ into usual care for adults with co-existing physical and mental NCDs in Colombia. | 
 - Cost in USD - Cost per Quality Adjusted Life Year (QALYs) gained - Changes in clinical variables (blood pressure, glycosylated haemoglobin, body weight and waist circumference). | 
 -6-month follow-up- - 12-month follow-up |

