15.11. Health Economics Analysis

15.11.1. **Measurement of health economic data**

Resource use specific to DD+ will capture both start-up (training, initial supervision, and device setup) and steady-state delivery (clinician time per DD+ session and documentation, routine/top-up supervision, app/support). These data will be obtained from site time sheets/logs and finance records in a health economics inventory form.

All other healthcare and patient-level resource use (whether under DD+ or usual care) will be collected at baseline, 6 months, and 12 months using a custom, interview-based health-economics inventory (CSRI-style) tailored to primary care for patients with co-occurring physical and mental NCDs in Colombia. Total cost per participant will be computed for 0–6 and 0–12 months from the health-system perspective.

15.11.2. **Value of resource utilization**

The amount of resource usage for each cost element will be combined with the relevant unit costs. Hourly trainer clinician wage rate will be used as the unit cost to calculate costs to training sessions and supervision, transportation expenses will be included in the implementation phase. On the other hand, hourly Health professional wage rates will be used to calculate the cost of their training, documentation and deliver DIALOG+. Unit costs for other health care services such as visits to a general practitioner, nurse, nutritionist, phycologist, social worker, psychiatrist, internal medicine or other subspecialist, and hospitalizations will be obtained from the tariff manual ISS 2001 + 30% and hospital bills (for sensibility analysis). The unit cost of the current medication prescribed to patients will be sourced from the Colombian drug price information system (SISMED in Spanish) based on the weighted price of each medication for the year. Costs will be reported in U.S. dollars (USD), using the average representative market exchange rate published by the Central Bank of Colombia (*Banco de la República*) for the study year. Sensitivity analyses will explore the impact of applying the minimum and maximum values of this exchange rate within the same year.

15.11.3. **Discounting**

No discount rate will be applied because the time horizon is 12 months.

15.11.4. **Geographical Jurisdictions**

The study will be carried out separately in 15 centers of Colombia.

15.11.5. **Measurement of effectiveness outcomes for health economic evaluation**

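### The primary cost model may be either Gamma with log link or log-normal, and these two options estimate different incremental costs

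*Protocol*

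**What the plan says.** The research question in section 7 begins: "What is the additional cost and cost-effectiveness of implementing and delivering". Table 1 in section 8 repeats this as a secondary objective, "Assess the additional cost and cost-effectiveness for implementation and delivery", and lists cost in USD among its outcome measures. Section 15.11.1 defines the variable ("Total cost per participant will be computed for" 0–6 and 0–12 months). It also says which costs belong to the intervention: "Resource use specific to DD+ will capture both start-up (training, initial supervision, and device setup) and steady-state delivery".

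Section 15.11.7 says "We will compute the ICER as the additional cost per additional QALY gained" and then gives the cost model: "Incremental costs will be estimated using mixed-effects generalized linear models appropriate for skewed data (primary: Gamma family with log link, or log-normal". No rule chooses between the two families. Section 15.11 mentions no return from the log scale to mean cost, and the sensitivity analyses in 15.11.9 vary tariffs, value sets, roll-out and horizon but not the cost model.

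Two other statements in 15.11.7 matter here. Arm differences in cost are first to be estimated without adjustment. The sentence after the cost model assigns incremental cost-effectiveness to linear mixed models.

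**The concern.** An additional cost per participant in USD, and the cost difference in an ICER, are differences in arithmetic means. A Gamma model with log link has the arithmetic mean as its target. A log-normal model has the mean of log cost as its target, so its arm effect is a ratio of geometric means. If the log-scale spread differs between arms, that ratio can move away from 1 although mean costs are equal.

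There is a specific reason to expect a difference in spread. Training, supervision, device and session costs fall on the DD+ arm only. A roughly constant add-on raises low-cost participants most on the log scale and so narrows the spread in that arm. The log-normal option would then tend to show DD+ as more costly than it is. Someone could follow the protocol to the letter and report the wrong quantity for a stated secondary objective, and no planned sensitivity analysis would show it.

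**Working it through.** **Numbers per arm.** Section 15.2 assumes: "A standard deviation of 0.9 for the MANSA and a correlation of 0.4 between baseline and follow-up measurements will be assumed", with a difference of 0.4, 90% power and two-sided 5%. Section 12.7 says "participants will be randomised in a 1:1 ratio to either DD+ or the control group". Then n = 2 × (1.960 + 1.282)² × 0.9² × (1 − 0.4²) / 0.4² = 89.4, so 90 per arm. With 20% attrition, 90 / 0.8 = 112.5, so 113 per arm and 226 in total. The plan's own figure reproduces. It supplies the n used below. The protocol gives no cost mean, SD or skewness, so every cost input below is an assumption.

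**Analytic check.** Let log cost be normal with SD s_C (control) and s_DD (DD+). The arithmetic mean is exp(μ + s²/2). Equal arithmetic means require μ_DD − μ_C = (s_C² − s_DD²)/2. The log-scale contrast has SE = √[(s_C² + s_DD²)/n].

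Example with s_C = 1.0, s_DD = 0.8, n = 113: shift = (1.00 − 0.64)/2 = 0.18; geometric mean ratio = e^0.18 = 1.197; SE = √(1.64/113) = 0.1205; probability that the interval lies wholly above no difference = 1 − Φ(1.960 − 0.18/0.1205) = 0.321. The nominal value is 0.025.

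| Log-SD control / DD+ | Geometric mean ratio | 90 per arm | 113 per arm |
|---|---|---|---|
| 1.0 / 1.0 | 1.00 | 0.025 | 0.025 |
| 1.0 / 0.9 | 1.10 | 0.099 | 0.113 |
| 1.0 / 0.8 | 1.20 | 0.265 | 0.321 |
| 1.2 / 1.0 | 1.25 | 0.266 | 0.322 |
| 1.2 / 0.8 | 1.49 | 0.749 | 0.838 |

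If DD+ has the larger log variance, the direction reverses: 0.8 / 1.2 gives 0.749 for DD+ apparently less costly at 90 per arm.

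**Mechanistic simulation.** Control cost is log-normal with mean M and log-SD s. DD+ cost is c + (1 − c/M) × a draw from the same distribution, so both arms have mean M and the true additional cost is zero. M is 500, 1,000 or 1,500; s is 0.8, 1.0 or 1.2; n is 113 per arm. Covariates and the practitioner random effect are left out; they do not change which mean is targeted. The table shows how often a two-sided 95% interval excludes no difference.

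| DD+ add-on c | Log-scale contrast | Raw means (Welch) |
|---|---|---|
| US$50 | 6–30% | 4–5% |
| US$100 | 7–71% | 5% |
| US$200 | 17–98% | 4–6% |

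Across simulation runs the top of the range is 98–99%. In the middle case (M = 1,000, s = 1.0, c = 200) the DD+ log-SD falls from 1.0 to 0.69, the geometric mean ratio is about 1.25, and the log-scale interval excludes no difference in 47–50% of trials against 5% for raw means. If session attendance varies (delivery cost of 0, one third, two thirds or all of US$200, full cost in two fifths), the log-scale figure drops to about 17–20%.

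**Gamma with log link.** In simulations of this kind it excludes no difference in about 4–9% of trials with robust standard errors.

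**Returning a log-normal fit to USD.** Using one common variance leaves a spurious difference of about +US$212 to +US$214 in the middle case. Using arm-specific variances leaves −7 to +5 per 500 where costs are truly log-normal (90 per arm). With a fixed add-on they are not exactly log-normal, and −6 to −45 per 500 remains.

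**The case against.** Several points on the other side have force.

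- **ICER and acceptability curve.** A reader might infer that a log-normal cost model biases these and the budget impact analysis. The text does not support that. Section 15.11.7 gives incremental cost-effectiveness to linear mixed models, which work on arithmetic means, and also plans unadjusted cost differences. It never says which of these supplies the ICER's cost difference. This point stands.
- **No cost test is planned.** A reader might infer that DD+ would be declared significantly more costly. Section 15.11 sets no null hypothesis or significance level for cost; inference rests on the cost-effectiveness plane and acceptability curve. The percentages above therefore describe how a model's interval behaves, not a planned decision. This also stands.
- **Unequal spread is not certain.** Section 13.3.1 allows for participants attending two or fewer of six sessions, so DD+ cost will vary between participants, and the effect shrinks when DD+ is cheap. This stands as a limit on size.
- **Extreme scenarios.** The top of the range needs DD+ to make up 40% of mean cost (200 of 500), exactly offset elsewhere. This is fair, and the range should be read as showing sensitivity and not as a forecast.
- **Back-transformation may be in the SAP.** It may, and its absence from the protocol is not the point. The point is that the protocol gives equal primary status to two models with different targets, and a common-variance back-transformation would not repair that.

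**Conclusion.** The point holds in limited form. Section 15.11.7 names two primary cost models that target different quantities, and only Gamma with log link directly targets the additional cost that sections 7 and 8 ask for. If the log-normal option is used and log-scale spread differs by arm, the reported incremental cost can be wrong: with a true difference of zero, its interval excludes no difference in about 6% to 99% of trials under the assumed inputs, against 4–6% for raw means. Low DD+ cost or uneven attendance puts the trial near the lower end. Equal log variances remove the error, and a larger log variance in DD+ reverses it. The Gamma option does not have this problem.

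The damage is to the incremental cost reported for a secondary objective. It reaches the ICER and acceptability curve only if their cost difference is taken from this model, which the protocol leaves open. This is an inexpensive improvement and does not touch the MANSA primary analysis.

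**What to change.** In section 15.11.7, remove the log-normal alternative from the primary cost model and state: *Primary: Gamma family with log link. Incremental cost is the difference in predicted arithmetic mean cost (USD) between arms, averaged over all randomised participants, with a robust or bootstrap 95% confidence interval. The same difference is the numerator of the ICER.* The last sentence also settles which of the analyses named in 15.11.7 feeds the ICER and the acceptability curve.

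A log-normal model can stay as a sensitivity analysis in 15.11.9, provided it is returned to the arithmetic mean with arm-specific retransformation.

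The cost is a wording change in the protocol or SAP, with the same data and software. The one drawback is a possibly wider interval, because arithmetic means of skewed costs are estimated less precisely than means of log costs.
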